2.2 Cohort 2: Newly Recruited Subjects

At least 25 subjects who have not previously been exposed to BAX326 will be enrolled (Cohort 2). Once eligibility criteria are confirmed, subjects will receive prophylactic treatment over a period of up to approximately 100 EDs to BAX326, or until BAX326 is approved in the subject's country, whichever occurs last, but no later than December 31, 2016. A limited number of patients may not have reached 100 EDs by that date and they will continue until they have reached approximately 100 EDs. The treatment regimen with BAX326 will be at the discretion of the investigator and will consist of one of the following treatment options:

- Standard prophylaxis with twice weekly prophylactic infusions of 50 IU/kg (range of 40-60 IU/kg, which may be increased to 75 IU/kg, in subjects ≥ 12 years of age; range of 40-80 IU/kg in pediatric subjects < 12 years), or
- modified prophylaxis determined by the investigator. The dose can be increased up to 100 IU/kg, if applicable; or
- PK-tailored prophylaxis. The maximum dose is 120 IU/kg.

2.3 Study Population

Previously treated patients (PTPs) with severe (FIX level $< 1\%$) or moderately severe (FIX level 1-2%) hemophilia B, who completed Pivotal Study 250901 or Pediatric Study 251101, and were between 12 and 65 years of age at the time of screening for Study 250901 or < 12 years old at the time of screening for Study 251101, will be recruited in this study (Cohort 1 patients).

In addition, at least 25 BAX326 naïve subjects with severe (FIX level $< 1\%$) or moderately severe (FIX level 1-2%) hemophilia B will be newly enrolled to ensure the evaluation of long-term safety and efficacy in approximately 100 PTPs (Cohort 2 patients).

2.4 Inclusion Criteria

2.4.1 Subjects Transitioning From Baxter Pivotal Study 250901 or Pediatric Study 251101 (Cohort 1)

Subjects who have completed Baxter Pivotal Study 250901 or Pediatric Study 251101 and meet **ALL** of the following criteria are eligible for this study:

1. Subject and/or legal representative has/have voluntarily provided signed informed consent.
2. Subject has completed Baxter Pivotal Study 250901 or Pediatric Study 251101.
3. Subject has not developed an inhibitory FIX antibody during Baxter Pivotal Study 250901 or Pediatric Study 251101.
4. Subject is human immunodeficiency (HIV) negative or is HIV+ with a viral load < 200 particles/ μ L $\sim < 400,000$ copies/mL.
5. Subject is immunocompetent as evidenced by a CD4 count ≥ 200 cells/ mm^3 .
6. If female of childbearing potential, subject presents with a negative pregnancy test and agrees to continue employing adequate birth control measures for the duration of the study.
7. Subject is willing and able to comply with the requirements of the protocol.

2.4.2 Newly Recruited Subjects (Cohort 2)

Newly recruited subjects who meet **ALL** of the following criteria are eligible for this study:

1. Subject and/or legal representative has/have provided signed informed consent.
2. Subject is 2 to 70 years old at the time of screening.
3. Subject is naïve to BAX326.
4. Subject has severe (FIX level $< 1\%$) or moderately severe (FIX level 1-2%) hemophilia B (based on the one stage activated partial thromboplastin time (aPTT) assay), as tested at screening at the central laboratory.
5. Subject aged ≥ 6 years has been previously treated with plasma-derived and/or recombinant FIX concentrate(s) for a minimum of 150 EDs.
6. Subject aged < 6 years has been previously treated with plasma-derived and/or recombinant FIX concentrate(s) for a minimum of 50 EDs.
7. Subject has no evidence of a history of FIX inhibitors.
8. Subject is immunocompetent as evidenced by a CD4 count ≥ 200 cells/ mm^3 at screening.

9. Subject is HIV negative or is HIV+ with a viral load < 200 particles/ μ L ~ < 400,000 copies/mL.
10. If female of childbearing potential, subject presents with a negative pregnancy test and agrees to employ adequate birth control measures for the duration of the study.
11. Subject is willing and able to comply with the requirements of the protocol.

2.5 Exclusion Criteria

2.5.1 Subjects Transitioning from Pivotal Study 250901 or Pediatric Study 251101 (Cohort 1)

Subjects who have completed Baxter Pivotal Study 250901 or Pediatric Study 251101 and meet **ANY** of the following criteria are not eligible for this study:

1. Subject received factor IX product(s) other than BAX326 upon completion of Baxter Pivotal Study 250901 or Pediatric Study 251101.
2. Subject has been diagnosed with an acquired hemostatic defect other than hemophilia B.
3. For subjects transferring from Pivotal Study 250901: The subject's weight is < 35 kg or > 120 kg.
4. Subject's platelet count is < 100,000/mL.
5. Subject has an abnormal renal function (serum creatinine > 1.5 times the upper limit of normal).
6. Subject has active hepatic disease with alanine aminotransferase (ALT) or aspartate aminotransferase (AST) levels \geq 5 times the upper limit of normal.
7. Subject is scheduled to receive during the course of the study, an immunomodulating drug (e.g. corticosteroid agents at a dose equivalent to hydrocortisone greater than 10 mg/day, or α -interferon) other than anti-retroviral chemotherapy.
8. Subject has a clinically significant medical, psychiatric, or cognitive illness, or recreational drug/alcohol use that, in the opinion of the investigator, would affect subject's safety or compliance.
9. Subject is planned to take part in any other clinical study, with the exception of BAX326 Surgery Study as described in this protocol, during the course of the Continuation Study.
10. Subject is a member of the team conducting this study or is in a dependent relationship with one of the study team members. Dependent relationships include

close relatives (ie, children, partner/spouse, siblings, parents) as well as employees of the investigator or site personnel conducting the study.

2.5.2 Newly Recruited Subjects (Cohort 2)

Newly recruited subjects who meet **ANY** of the following criteria are not eligible for this study:

1. Subject has a history of FIX inhibitors with a titer ≥ 0.6 Bethesda Units (BU) (as determined by the Nijmegen modification of the Bethesda assay or the assay employed in the respective local laboratory) at any time prior to screening.
2. Subject has a detectable FIX inhibitor at screening, with a titer ≥ 0.6 BU as determined by the Nijmegen modification of the Bethesda assay in the central laboratory.
3. Subjects ≥ 12 years of age: Subject's weight is < 35 kg or > 120 kg.
4. Subject has a history of allergic reaction, eg, anaphylaxis, following exposure to FIX concentrate(s).
5. Subject has a known hypersensitivity to hamster proteins or rFurin.
6. Subject has evidence of an ongoing or recent thrombotic disease, fibrinolysis or disseminated intravascular coagulation (DIC).
7. Subject has an abnormal renal function (serum creatinine > 1.5 times the upper limit of normal).
8. Subject has severe chronic liver disease as evidenced by, but not limited to, any of the following: International Normalized Ratio (INR) > 1.4 hypoalbuminemia, portal vein hypertension including presence of otherwise unexplained splenomegaly and history of esophageal varices.
9. Subject has active hepatic disease with ALT or AST levels > 5 times the upper limit of normal.
10. Subject has been diagnosed with an inherited or acquired hemostatic defect other than hemophilia B.
11. Subject's platelet count is $< 100,000/\text{mL}$.
12. Subject has a clinically significant medical, psychiatric, or cognitive illness, or recreational drug/alcohol use that, in the opinion of the investigator, would affect subject's safety or compliance.
13. Subject is currently receiving, or is scheduled to receive during the course of the study, an immunomodulating drug (eg, corticosteroid agents at a dose equivalent

to hydrocortisone greater than 10 mg/day, or α -interferon) other than anti-retroviral chemotherapy.

14. Subject has participated in another investigational study within 30 days of enrollment.
15. Subject is a member of the team conducting this study or is in a dependent relationship with one of the study team members. Dependent relationships include close relatives (ie, children, partner/spouse, siblings, parents) as well as employees of the investigator or site personnel conducting the study.

2.6 Sample Size and Power Calculations

The sample size is not based on statistical consideration and is determined by the number of subjects of the BAX326 pivotal protocol 250901 and the pediatric protocol 251101, who are willing to participate in this study and meet the eligibility criteria as well as regulatory requirements.

2.7 Randomization and Blinding

This section is not applicable.

2.8 Study Stopping Rules

This study will be halted, pending further review by the sponsor, or stopped under the following circumstances:

- If two or more subjects develop a high titer inhibitory antibody > 5 BU confirmed by the central laboratory, or if two or more subjects develop anaphylaxis following exposure to BAX326 in studies BAX326 Pivotal 250901, BAX326 Pediatric 251101, and BAX326 Continuation 251001, the transition to BAX326 Continuation will be halted. Within 2 weeks of receipt of the second report, Baxalta may decide to halt the study.
- The study may be stopped following any of the planned interim safety reviews or at any time by the sponsor in case of unacceptable risks to subjects, in particular in case of inhibitor development, thrombotic events, or anaphylaxis.

2.9 Data Monitoring Committee

The safety of BAX326 in this study will be monitored by an independent Data Monitoring Committee (DMC) as scheduled until the end of 2015. The DMC is a group of individuals with pertinent expertise that reviews on a regular basis accumulating data from an ongoing clinical study. For this study, the DMC will be composed of recognized experts in the field of hemophilia clinical care and research who are not actively recruiting subjects, and an independent statistician.

The sponsor will formally convene this panel for review of the study data at least once per year until completion of the study. From the beginning of 2016 onwards, the DMC chair will no longer review all SAEs for all subjects as sufficient positive safety data from pre- and post-marketing BAX326 exposures are already available.

The study may be stopped at any time by the sponsor in case of unacceptable risks to subjects, in particular in case of inhibitor development, thrombotic events, or anaphylaxis.

3. STUDY OUTCOME MEASURES

3.1 Primary Outcome Measure

The primary outcome measure is AEs possibly or probably related to IP.

3.2 Secondary Outcome Measures

3.2.1 Hemostatic Efficacy

- Treatment of bleeding episodes:
 - Number of infusions per bleeding episode
 - Overall hemostatic efficacy rating at resolution of bleed
- Prophylaxis:
 - Annualized bleeding rate (ABR)
- Consumption of BAX326:
 - Number of infusions and weight-adjusted consumption per month and per year
 - Weight-adjusted consumption per event (for prophylaxis and on-demand)

3.2.2 Safety and Immungenicity

- Development of inhibitory and total binding antibodies to FIX
- Development of antibodies to CHO proteins and rFurin
- Occurrence of severe allergic reactions, e.g. anaphylaxis
- Occurrence of thrombotic events
- Clinically significant changes in routine laboratory parameters (hematology and clinical chemistry), and vital signs

3.2.3 Pharmacokinetics

- IR (incremental recovery) over time

If subject receives a PK-tailored dose regimen and did not participate in the PK portion of the BAX326 pivotal or BAX326 surgery study, then the following parameters will be calculated:

- AUC_{0-∞} (area under the plasma concentration time curve from time 0 to infinity), T_{1/2} (elimination phase half-life), MRT (mean residence time), CL (clearance), V_{ss} (volume of distribution at steady state) and IR (incremental recovery)

3.2.4 Health-Related Quality of Life and Pharmacoeconomics

The assessment of HR QoL based on 4 questionnaires will be performed every 6 months ± 1 week. Newly recruited subjects will have their first HrQoL assessment including Patient Activity Level performed prior to or following the first infusion with BAX326, thereafter every 6 months.

The capture of health resource use will be performed by a named member of study site staff every 3 months ± 1 week. Newly recruited subjects will have their first health resource use capture prior to or following the first infusion with BAX326, thereafter at every 3 months ± 1 week.

Data on HR QoL and Health Resource Use will be collected using the instruments shown in the following table, with some instruments having an age specific version.

Table 1: Age specific instruments used for HR QoL and Health Resource Use

Instrument	Age Group (Age at the time of screening for Pediatric Study 251101 for Cohort 1 subjects or at the time of screening for Study 251001 for Cohort 2 subjects)			
	2 to 7 years	8 to 11 years	12 to 16 years	17 years and older
Leisure Time Exercise Questionnaire (Patient Activity Level)	Yes	Yes	Yes	Yes
Health Resource Use	Yes	Yes	Yes	Yes
Generic: PedsQL™	Yes: Parent-proxy versions (age groups: 2-4years and 5-7 years)	Yes: Child version	Yes	NA
Disease-specific: Haemo-QoL	NA	Yes: Short version	Yes: Short version	Yes
General pain assessment through a visual analog scale (VAS)	NA	NA	Yes	Yes
Health utility: EQ-5D	NA	NA	Yes	Yes
Generic: SF-36	NA	NA	NA	Yes

3.2.5 Exploratory Outcomes Measures

- If applicable, TGA parameters over 72 hours during PK (lag time, time to peak thrombin generation, peak thrombin generation, endogenous thrombin potential [ETP])
- TGA parameters pre- and post-infusion concurrent with IR determination for FIX activity in a subset of subjects receiving twice-weekly standard or modified prophylaxis including PK-tailored prophylaxis with BAX326 as well as at some selected time points during prophylactic treatment

4. ANALYSIS SETS

4.1 Full Analysis Set

The Full Analysis Set (FAS) will be comprised of all subjects who are exposed to any amount of IP. For subjects who discontinue before reaching 100 EDs, data will be included up through the day of discontinuation. The FAS will be used for all analyses unless otherwise stated.

4.2 Per Protocol Analysis Set

The Per Protocol Analysis Dataset (PPAS) is defined as a subset of the Full Analysis Set.

1. Transitioning Subjects:

Subjects who did not meet study inclusion criteria

- The subject has severe (FIX level <1%) or moderately severe (FIX level $\leq 2\%$) hemophilia B (based on the one stage activated partial thromboplastin time (aPTT) assay), as tested at screening at the central laboratory
- The subject has not developed an inhibitory FIX antibody during Baxter clinical study 250901
- The subject has not developed an inhibitory FIX antibody during Baxter Pivotal Study 250901 or Pediatric Study 251101

or met the exclusion criteria

- The subject has been diagnosed with an acquired hemostatic defect other than hemophilia B.
- The subject's platelet count is $<100,000/\text{mL}$.

will be excluded from the PPAS.

2. Newly Recruited Subjects:

Subjects who did not meet study inclusion criteria

- The subject has severe (FIX level <1%) or moderately severe (FIX level 1-2%) hemophilia B (based on the one stage activated partial thromboplastin time (aPTT) assay), as tested at screening at the central laboratory
- The subject has no evidence of a history of FIX inhibitors

or met the exclusion criteria

- The subject has a history of FIX inhibitors with a titer ≥ 0.6 Bethesda Units (BU) (as determined by the Nijmegen modification of the Bethesda assay or the assay employed in the respective local laboratory) at any time prior to screening
- The subject has a detectable FIX inhibitor at screening with a titer ≥ 0.6 BU as determined by the Nijmegen modification of the Bethesda assay in the central laboratory
- The subject has severe chronic liver disease as evidenced by, but not limited to, any of the following: International Normalized Ratio (INR) > 1.4 , hypoalbuminemia, portal vein hypertension including presence of otherwise unexplained splenomegaly and history of esophageal varices.
- The subject has been diagnosed with an inherited or acquired hemostatic defect other than hemophilia B.
- The subject's platelet count is $< 100,000/\text{mL}$

will be excluded from the PPAS.

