## 9. SUBJECT SELECTION, WITHDRAWAL, AND DISCONTINUATION

### 9.1 Inclusion Criteria

#### 9.1.1 Subjects Transitioning From Baxter Pivotal Study 250901 or Pediatric Study 251101 (Cohort 1)

Subjects who have completed Baxter Pivotal Study 250901 or Pediatric Study 251101 and meet **ALL** of the following criteria are eligible for this study:

- Subject and/or legal representative has/have voluntarily provided signed informed consent.
- Subject has completed Baxter Pivotal Study 250901 or Pediatric Study 251101.
- Subject has not developed an inhibitory FIX antibody during Baxter Pivotal Study 250901 or Pediatric Study 251101.
- Subject is human immunodeficiency (HIV) negative or is HIV+ with a viral load  $< 200$  particles/ $\mu$ L  $\sim < 400,000$  copies/mL.
- Subject is immunocompetent as evidenced by a CD4 count  $\geq 200$  cells/ $mm^3$ .
- If female of childbearing potential, subject presents with a negative pregnancy test and agrees to continue employing adequate birth control measures for the duration of the study.
- Subject is willing and able to comply with the requirements of the protocol.

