#### **10.3.1 Subjects Transitioning from BAX326 Pivotal or BAX326 Pediatric Study (Cohort 1)**

The screening visit will be performed on the same day as the completion/ termination visit for the 250901 (pivotal) or 251101 (pediatric) protocol.xx The Informed Consent will be obtained before any procedures related to the BAX326 Continuation study are performed. Tests performed for the BAX326 completion/ termination visit of the main study will not be repeated for screening in Study 251001, and the relevant data obtained for the 250901 or 251101 completion/termination visit will be transcribed to the screening visit eCRF.

Following the screening visit, subjects will continue receiving BAX326 until his/her eligibility for the study is confirmed. If the eligibility criteria are not met, a completion/termination visit will be performed at the Week 4 $\pm$ 1 visit following screening.

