5.2 Handling of Missing, Unused, and Spurious Data

Statistical techniques will not be used to identify and exclude any observations as outliers from the analyses. If data are considered spurious (e.g. for lack of biological plausibility), it will be documented along with the reason for exclusion and the analyses from which the data were excluded.

1. For subjects with multiple screening visits resulting in multiple values, the most recent screening visit will be used for analysis.
2. Subjects who withdraw prior to the last planned observation in the study period will be included in the analyses up to the time of withdrawal.
3. Extra measurements (such as unscheduled or repeat assessments) will not be included in the descriptive statistics, but will be included in subject listings.
4. If a subject's weight is missing from any infusion record, the subject's last recorded weight will be used to calculate the weight-adjusted dose.

Outcome specific handling of missing data are described in the relevant section. Unless otherwise specified, no action will be made to handle missing data (observed case).

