5.5 Changes from the Planned Statistical Analysis in Protocol

The following changes from the planned statistical analysis in the protocol were made:

- In some instances, techniques will be used to adjust for missing data.
- In addition to the Full Analysis Set, a Per Protocol Analysis Set and a Pharmacokinetic Full Analysis Set were added.
- Pharmacokinetic parameters will be calculated using non-compartmental analysis (NCA), rather than a model combining data from this and previous studies, due to the lack of a suitable model.
- In order to determine the incremental recovery (IR) over time and see if antibodies have affected the recovery following long-term exposure, it is important to compare the end of study IR with the baseline IR. Therefore the IR will be summarized for baseline and end of study only rather than for all available time points.

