6.2 Demographic and Baseline Characteristics

Demographic data will be summarized descriptively and listed by treatment regimen as well as for all treatment regimens together:

- Age at Screening
- Age at Screening of Parent Protocol (applicable only for transitioning subjects)
- Gender
- Ethnicity (for US only)
- Race
- Height [cm] at Screening
- Weight [kg] at Screening
- Body mass index (BMI) [kg/m^2] at Screening.

Demographic variables will be summarized for the FAS, the PPAS and the PKFAS.

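### SAP 4.2 drops transitioning subjects with FIX above 2% at an unnamed screening from the per-protocol set, although Cohort 1 has no FIX-level criterion; if continuation screening is used, residual BAX326 could exclude eligible subjects

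*SAP*

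**What the plan says.** The PPAS exists only in the SAP. Protocol 14.2 uses the Full Analysis Set (FAS) throughout, and SAP 5.5 records the change: "In addition to the Full Analysis Set, a Per Protocol Analysis Set and a Pharmacokinetic Full Analysis Set were added". SAP 4.2 is therefore the only definition of the set.

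For transitioning subjects, SAP 4.2 excludes those who fail study inclusion criteria. The first criterion listed is severe (below 1%) or moderately severe (2% or less) hemophilia B by the one-stage assay, "as tested at screening at the central laboratory". A subject above 2% is therefore excluded. The next line is "The subject has not developed an inhibitory FIX antibody during Baxter clinical study 250901". The line after that covers both parent studies, in the same terms as protocol 9.1.1: "Subject has not developed an inhibitory FIX antibody during Baxter Pivotal Study 250901 or Pediatric Study 251101".

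Protocol 9.1.1 and SAP 2.4.1 each give seven inclusion criteria for Cohort 1. They include "Subject has completed Baxter Pivotal Study 250901 or Pediatric Study 251101" and the inhibitor criterion, but no FIX level. A FIX-level criterion applies to Cohort 2 only (protocol 9.1.2, SAP 2.4.2).

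**The concern.** The SAP's exclusion rule cites an inclusion criterion that the SAP's own list does not contain, and it leaves the reference visit open. A programmer cannot tell from SAP 4.2 which FIX value to use.

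The choice matters because the two values differ in kind. At parent-study screening the subject had not yet received BAX326. Continuation screening falls on the day of the parent study's termination visit, so a subject on prophylaxis is then on BAX326.

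If the later value is used, the rule can remove subjects who meet every current Cohort 1 criterion. It would do so selectively, taking those who clear the drug slowly or whose own level lies near 2%. Protocol 6.1 cites a pooled factor VIII analysis that links bleeding to time below 1%, adds that half-life mattered more than recovery for that time, and expects the same in hemophilia B. On that reasoning the removed subjects may differ in bleeding from those kept, and the PPAS would not be a neutral check on the FAS.

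**Working it through.** **Which screening.** The passages point in different directions.
- Towards this study: SAP 6.2 lists age at screening of the parent protocol separately from age at screening, so the unqualified word there means this study.
- Towards the parent study: protocol 6.1, in describing PK-tailored dosing, places a transitioning subject's baseline FIX at parent-study screening. Protocol 12.7.5.1 limits the eligibility FIX test at screening to newly recruited subjects.

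**What value exists at continuation screening.** Protocol 10.3.1: "Tests performed for the BAX326 completion/ termination visit of the main study will not be repeated for screening in Study 251001". Protocol Table 21.3-1 has a FIX recovery row for Cohort 1 but no separate FIX activity row; Table 21.4-1 for Cohort 2 has one. The only candidate is the pre-infusion recovery sample, taken at least 5 days (120 h), preferably 7 days (168 h), after the previous dose (protocol 21.1, item 1a).

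**Can residual BAX326 exceed 2%?** The plan gives no figure to reproduce. Inputs:
- Last dose 50 IU/kg (protocol 6.4.1; pivotal range 40 to 63 in 6.1).
- Recovery 0.87 (pivotal mean, 6.4.1).
- Half-life: median 24.58 h, range 15.83 to 52.34 h (PK portion, 28 subjects, 6.4.1).
- Terminal-phase intercept as a fraction f of the peak. The documents do not give it; assumed 1 (mono-exponential), 0.6 or 0.3.

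Residual = 50 × 0.87 × f × 2^(−h/T) = 43.5 f × 2^(−h/T), for half-life T at h hours.

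With f = 1:
- Median half-life: 43.5 × 2^(−120/24.58) = 1.48% at 5 days; 0.38% at 7 days.
- Longest half-life: 43.5 × 2^(−120/52.34) = 8.88% at 5 days; 4.70% at 7 days.

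The total passes 2% when T > h / log2(43.5 f / x), where x is 2 minus the subject's own level. For an own level near zero and f = 1: 120 / log2(21.75) = 120 / 4.443 = 27.0 h, and 168 / 4.443 = 37.8 h.

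| Own level | Wash-out | f = 1 | f = 0.6 | f = 0.3 |
|---|---|---|---|---|
| near 0% | 5 days | 27.0 h | 32.4 h | 44.3 h |
| near 0% | 7 days | 37.8 h | 45.3 h | 62.1 h |
| 1.5% | 5 days | 18.6 h | 21.0 h | 25.5 h |
| 1.5% | 7 days | 26.1 h | 29.4 h | 35.7 h |

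Every threshold but one (62.1 h) lies inside the observed half-life range. The 27.0 h figure becomes 29.1 h at 40 IU/kg and 25.1 h at 63 IU/kg.

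**The case against.** **The line may mean parent-study screening.** It concerns disease severity, and continuation screening has no severity test for Cohort 1. On that reading residual BAX326 does not enter and nobody is wrongly excluded. This stands as a real alternative, so a reader should not infer that the SAP certainly means continuation screening. SAP 5.2 does not settle it: "For subjects with multiple screening visits resulting in multiple values, the most recent screening visit will be used for analysis" reads naturally as re-screening within this study.

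**Severity belongs to the population.** Protocol 6.3 and SAP 2.3 describe Cohort 1 as severe or moderately severe, so checking severity in a per-protocol set is reasonable in principle. That is fair, but it does not create a listed criterion tested at this study's screening.

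**The list may merge protocol versions.** The amendment log shows that a FIX-level criterion was once present for these subjects and was removed because severity had been confirmed in the parent study. Someone enrolled after the removal cannot fail it. This probably explains how the line arose, but SAP 4.2 limits no line to an enrolment version.

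**Mono-exponential decay overstates the residual.** This also has force. Protocol 6.1 reports, for another recombinant FIX, that 1% troughs could normally be held by dosing every 2 to 3 days. With 50 IU/kg, recovery 0.75 and half-life 20 h, FIX stays above 1% for 20 × log2(37.5) = 105 h if f = 1, and for 20 × log2(11.25) = 70 h if f = 0.3. The simulated dose is not stated, but the lower f fits better. At f = 0.3, a subject with almost no FIX of their own passes 2% only above 44.3 h at 5 days, and at no observed half-life at 7 days.

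**Conclusion.** The point holds as an inconsistency with an undefined reference visit. That SAP 4.2 applies a criterion absent from SAP 2.4.1 and protocol 9.1.1, and names no study, follows from the text alone. That eligible subjects could be excluded depends on using the continuation-screening value. Given that, crossing 2% at 5 days is possible at every f tried. At 7 days it needs a long half-life or an own level near 2%.

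A reader might infer that a sizeable share of Cohort 1 would be lost. The documents do not support any share: it would rest on an assumed f, an assumed half-life distribution and 28 pivotal-study subjects, with no BAX326 half-lives given under 12 years. Subjects treated on demand (14 of 73 in the pivotal study) are largely unaffected.

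Nor does the point undermine the study's conclusions. SAP 7 makes the FAS analysis primary for efficacy, SAP 8 puts safety on the FAS, and the primary outcome is related adverse events. Only PPAS output is exposed: the supportive efficacy tables and that set's demographic summary.

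It would also be wrong to extend the point to antibodies. SAP 8.2 compares titers with this study's screening visit, which is a legitimate within-study reference.

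**What to change.** In SAP 4.2, for transitioning subjects:
- Delete the FIX-level line, or tie it explicitly to the parent-study screening value.
- Remove the inhibitor line that names study 250901 only, since the next line covers it. If any line is meant only for subjects enrolled under a particular protocol version, say so beside it.

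In SAP 7.2.2, which splits ABR by FIX activity at screening without naming the study, use the same reference: parent-study screening for Cohort 1, this study's screening for Cohort 2.

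Deletion costs a wording change. Tying the line to parent-study screening, and the SAP 7.2.2 clarification, also require merging in the parent-study FIX value. One drawback remains: that value may carry residual from an earlier FIX product, because the wash-out before parent-study screening is not given in these documents.
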